5. SUBJECT ENROLLMENT

Before subjects begin participation in any study-specific activities/procedures, Amgen requires a copy of the site's written institutional review board/independent ethics committee (IRB/IEC) approval of the protocol, informed consent form (ICF), and all other subject information and/or recruitment material, if applicable (see [Section 11.2](#)). A written main study ICF must be signed and personally dated by the subject or by the subject's legally acceptable representative and by the person who conducted the informed consent discussion before any protocol specified procedure is performed.

Each subject who enters into the screening period for the study (defined as the point when the subject or the subject's legally acceptable representative signs the IRB/IEC approved main study ICF) receives a unique subject identification number before any study-related activities/procedures are performed. The subject identification number will be assigned by the IVRS/IWRS. This number will be used to identify the subject throughout the clinical study and must be used on all study documentation related to that subject.

The subject identification number must remain constant throughout the entire clinical study; it must not be changed after initial assignment, including if a subject is rescreened.

A subject is considered enrolled when the investigator decides that the subject has met all eligibility criteria, and has entered enrollment into the IVRS/IWRS. The investigator is to document this decision and date in the subject's medical record and in/on the enrollment electronic case report form (eCRF).

During the enrollment call, the subject will be categorized to: (a) those expecting to receive blinatumomab as a first salvage treatment or (b) those expecting to receive blinatumomab as a second or greater salvage treatment.

5.1 Randomization/Treatment Assignment

This is an open-label, non-randomized study. The investigator, the subject, and the sponsor will know the treatment. All subjects in this study will receive blinatumomab treatment.

The treatment assignment date is to be documented in the subject's medical record and on the enrollment eCRF.

Approved

6. TREATMENT PROCEDURES

6.1 Classification of Product(s) and/or Medical Device(s)

The Amgen Investigational Product (IP) used in this study is blinatumomab.

The Investigational Product Instruction Manual (IPIM), a document external to this protocol, containing detailed information regarding the storage, preparation, and administration of blinatumomab will be provided to each investigational site.

All other protocol-specified therapies including, pre-phase therapies, that are commercially available are not provided or reimbursed by Amgen (except if required by local regulation). The Investigator will be responsible for obtaining supplies of these protocol-specified therapies.

6.2 Investigational Product

6.2.1 Amgen Investigational Product

Blinatumomab will be manufactured by Boehringer Ingelheim Pharma GmbH & Co KG and packaged by Amgen and distributed using Amgen clinical study drug distribution procedures.

Blinatumomab will be supplied as single-use glass injection vials as a sterile, preservative-free, white to off-white, lyophilized powder for reconstitution and administration by IV infusion. Each vial contains blinatumomab with additional excipients and buffers including citric acid monohydrate, trehalose dihydrate, lysine hydrochloride and polysorbate 80, pH 7.

To prepare blinatumomab for IV infusion, the lyophilized powder is reconstituted with sterile water for injection. The reconstituted solution is added to an infusion bag containing 0.9% NaCl and a product-specific stabilizer (IV Solution Stabilizer). The IV solution stabilizer functions to prevent adsorption of blinatumomab to surfaces of the infusion components. The IV Solution Stabilizer is supplied in a single-use glass injection vials as a sterile, preservative-free, clear, colorless-to-slightly-yellow liquid concentrate.

Sterile water for injection and supplies required for reconstitution and injection of blinatumomab will not be provided to clinical sites.

For information surrounding the use of a continuous infusion pump, refer to [Section 6.11](#).

6.2.2 Dosage, Administration, and Schedule

Blinatumomab is administered as a CIVI.

A single cycle of blinatumomab treatment is 6 weeks in duration, which includes 4 weeks of blinatumomab CIVI followed by a 2 week treatment-free interval. The treatment-free interval may be prolonged by up to 7 days, if deemed necessary by the investigator.

In the first induction cycle, the initial dose of blinatumomab will be 9 µg/day for the first 7 days of treatment (to mitigate for potential cytokine release syndrome [CRS] and CNS events associated with introduction to blinatumomab) which then will be escalated (dose step) to 28 µg/day starting on day 8 (week 2) through day 29 (week 4). For all subsequent cycles (beginning with the second induction cycle and continuing through consolidation, for applicable subjects) 28 µg/day will be the dose for all 4 weeks of continuous treatment.

The drug administration should not be interrupted, if possible. In case of infusion interruption, due to any technical or logistic reason, the interruption should be as short as possible and the infusion continued at the earliest time possible. Every interruption longer than 1 hour should be documented. If the interruption is longer than 4 hours, restart of the infusion should be performed in the hospital, under the supervision of the investigator. The subject should be observed overnight for possible side effects after the restart, either in the hospital or in the outpatient setting as applicable. Administration of dexamethasone premedication as described in [Table 8](#). It is recommended, if possible, that the infusion duration before and after an interruption should total 28 days per treatment cycle.

The daily blinatumomab dose may be up to 10% lower or higher in order to account for possible pump inaccuracies. For dose modifications in case of adverse events see [Section 6.5](#).

A dose of up to 10% higher than the intended dose may not require specific intervention. In case of overdose or medication error, the infusion should be immediately stopped. Routine supportive and symptomatic care according to standard medical practice is recommended. Once the subject is stabilized and no clinically relevant safety findings due to blinatumomab are observed, resumption of blinatumomab at a correct dose can be considered after consultation with the Amgen medical monitor.

If the overdose results in an adverse event, the subject should be followed carefully until all signs of toxicity are resolved and the adverse event/s should be recorded/reported.

The dose, start and stop date/time, and lot number of protocol-specified therapy is to be recorded on each subject's eCRF.

6.2.2.1 Blinatumomab Inpatient Dosing

It is strongly recommended that subjects are hospitalized at least during the first 9 days (1 week plus 2 days following dose step) of the first cycle and the first 2 days of the following cycle.

The hospitalization time depends on investigator's judgment, as well as safety and tolerability of blinatumomab. However, the hospitalization must span at least the first 2 days after treatment start in the first 2 cycles and after dose step. For cycle 3 and beyond, subjects will at least come in for an 8 hours outpatient observation followed by daily outpatient follow-ups during the subsequent 2 days. Additional hospitalization may be necessary, eg, in case of serious adverse events or restart of treatment after treatment interruptions due to adverse events.

The infusion bags will be changed by site nursing personnel trained on the protocol and on the proper administration of blinatumomab. Close monitoring during the first 48 hours of treatment in the first 2 cycles will be indicated because of the potential adverse events associated cytokine release triggered by the administration of blinatumomab.

Nurses/physicians trained in emergency medicine should be available for immediate intervention in case of complications.

6.2.2.2 Blinatumomab Outpatient Dosing

After a subject meets the minimum criteria for inpatient administration and monitoring as described in the above section, and if a subject is deemed stable by the investigator, continuation of blinatumomab infusion may continue as an outpatient.

In the outpatient setting, either the subject will return to the study site for changes of the infusion bag or the subject will be visited by a well-trained ambulant/home care service provider at specific intervals to change the infusion bag. The subject and the ambulant/home care service provider will be trained and will receive written instructions for storage of the IV bags.

For the ambulant/home care service provider, study-specific requirements and recording of source documentation must be completed before any study-related tasks are started. A comprehensive list of all home care services, including but not limited to the storage, handling, and administration of blinatumomab as well as mandatory procedural and data collection requirements will be separately provided in a home health care manual.

Following each visit, this information will be documented on the ambulant/home care services visit worksheet and forwarded to the investigator.

In case of any adverse event in the outpatient setting, the ambulant/home care service provider should directly contact the investigator at the study center for further management. Any unexpected or unusual events as well as any deviations will be communicated promptly to the investigator. The ambulant/home care service professionals provide 24 hour emergency on-call service.

In addition, the subject will visit the study center for the examinations according to the Schedule of Assessments ([Table 9](#)).

In the event of drug interruptions of > 4 hours, the restart of the infusion should be performed in the clinic/hospital under the supervision of the investigator.

6.3 Dexamethasone Premedication

Premedication with dexamethasone is intended to prevent CRS events associated with blinatumomab treatment.

[Table 7](#) below summarizes dexamethasone use before blinatumomab treatment during different phases of the study. Please also refer to appropriate protocol sections for specific details as not all information is contained within [Table 7](#). The date and time of infusion bag changes, all infusion start and stop times, and any dose modifications should also be recorded accurately.

Approved

Table 7. Dexamethasone Premedication

Treatment Phase	Target Subject:	Dexamethasone Dose	Comments
Pre-phase Therapy Before Blinatumomab	
During screening and before the start of treatment:
 
Mandatory for:
 
 Proportion of Blasts exceeds approximately 50%, or Peripheral blast count $\geq 15,000/\mu\text{L}$ 
Recommended for:
 
 LDH indicates rapidly progressing disease, or Extramedullary high tumor load 	Dexamethasone orally or IV up to 10 mg/m ² /day can be administered during screening and pre-phase until cycle 1 day 1. If indicated dexamethasone dose can be increased to an absolute maximum of 24 mg/day	See protocol Section 6.3.1
Pre-dose Dexamethasone before each Blinatumomab Treatment	All subjects (before each cycle and dose step/increase)	Dexamethasone 20 mg IV: within 3 hours before start of treatment in each treatment cycle, and within 3 hours before dose step (increase).	See protocol Section 6.3.2
Infusion Interruption/Dose Modification Due to Adverse Event	Subjects who interrupt treatment > 4 hours	Dexamethasone 20 mg IV: within 3 hours before restart of treatment	See protocol Section 6.5
In case of signs of cytokine release (CRS)	Subjects with signs of CRS	Dexamethasone orally or IV at a maximum dose of 8 mg, 3 times per day. Reduce step-wise over 4 days or as otherwise appropriate per the investigator.	See protocol Section 6.5
Infusion Interruption/Dose Modification Due to CNS Events	Subjects with CNS-related adverse event	Dexamethasone up to 24 mg/day for up to 3 days. Reduce step-wise over 4 days or as otherwise appropriate per investigator.	See protocol Section 6.5

Approved

6.3.1 Pre-phase Therapy Before Blinatumomab Treatment

Premedication with dexamethasone is intended to prevent CRS events associated with blinatumomab treatment. Please refer to [Table 7](#) for pre-phase dosing instructions with dexamethasone.

For this study, mandatory pre-phase therapy with dexamethasone is required before blinatumomab treatment if one or more of the following criteria are met:

- Proportion of blasts (determined by cytomorphology) exceeds approximately 50%, or
- peripheral blood blast count $\geq 15,000/\mu\text{L}$.

Pre-phase therapy with dexamethasone is recommended before blinatumomab treatment if, in the opinion of the investigator:

- LDH indicates rapidly progressing disease, or
- signs of extramedullary disease show high tumor load.

Pre-phase dexamethasone at a dose up to 10 mg/m²/day during screening. If clinically indicated, the dexamethasone dose can be increased to an absolute maximum dose of 24 mg/day.

If the subject received dexamethasone (up to 24 mg/day) for other reasons than pre-phase within 14 days before the start of screening, further pre-phase treatment with dexamethasone is not required. However, premedication with dexamethasone is required within 3 hours before the start of treatment in each treatment cycle and within 3 hours before the dose step as described in [Table 7](#).

It should be noted that in cases of ALL that are refractory to dexamethasone treatment, a preventative effect on CRS can still be achieved. If a subject is refractory to dexamethasone, a pre-phase is not mandatory, but dexamethasone up to a maximum dose of 24 mg/day should be administered at least for the first 2 days of treatment with step-wise reduction afterwards.

Subjects who should receive dexamethasone treatments of at least 24 mg/day and who have already received the mandatory 20 mg IV premedication dose before blinatumomab infusion at day 1, may receive the remaining balance of dexamethasone up to a maximum of 24 mg/day.

6.3.2 Pre-dose Dexamethasone Before Each Blinatumomab Treatment

Within 3 hours before the start of treatment in each treatment cycle and within 3 hours before dose step, mandatory premedication with dexamethasone at 20 mg IV is required for the prevention of CRS resulting from blinatumomab.

6.4 CSF Prophylaxis Before Blinatumomab Treatment

Within 14 days before the start of blinatumomab and following each induction and consolidation treatment cycle (after BM aspiration on day 29) a mandatory CSF

prophylaxis consisting of an intrathecal regimen according to institutional or national guidelines will be administered (eg, methotrexate 12 to 15 mg, cytosine arabinoside 40 mg, and dexamethasone 4 mg or equivalent steroid dose). In case of anticipated safety risks caused by lumbar puncture, eg, in case of thrombocytopenia, CSF prophylaxis may be omitted.

6.5 Dose Modifications (Interruptions, Withholdings, and Criteria for Restarting Treatment)

Table 8. Instructions for Treatment Interruption, Dose Modification and Restart

Toxicity	Grade	Instructions for Treatment Interruption and Restart
Cytokine Release Syndrome (CRS)	3	
 Interrupt blinatumomab and administer corticosteroids (refer to Table 7) Restart blinatumomab at 9 µg/day once improved to grade ≤ 1 or to baseline Dose step to 28 µg/day after 7 days if toxicity does not recur
	4	
 Permanently discontinue blinatumomab
Neurologic Events	3	
 Interrupt blinatumomab for at least 72 hours and administer corticosteroids (refer to Table 7) Restart blinatumomab at 9 µg/day once improved to grade ≤ 1 or to baseline Dose step back to 28 µg/day after 7 days if toxicity does not recur Permanently discontinue if: 
 Initial event occurred at 9 µg/day Initial grade 3 neurologic event does not improve to ≤ grade 1 within 7 days OR Grade 3 neurologic event reoccurs at the lower dose level within 7 days of reinitiation
	4	
 Permanently discontinue blinatumomab

Footnotes provided on last page of table

Page 1 of 3

Approved

Table 8. Instructions for Treatment Interruption, Dose Modification and Restart

Toxicity	Grade	Instructions for Treatment Interruption and Restart
	Seizures ^a	
 Interrupt blinatumomab, administer corticosteroids (refer to Table 7) and anti-seizure medication per local practice For restart, refer to grade 3 neurologic events above for dose level rules for reinitiation Do not reinitiate blinatumomab until 7 days after the last seizure and after therapeutic levels of anti-seizure medication are likely to have been achieved Permanently discontinue blinatumomab if a second seizure occurs with reinitiation of blinatumomab at any dose
Elevated liver enzymes	Not applicable	
 Interrupt blinatumomab (refer to Section 6.7.2) if any one of the following occurs: 
 TBL > 3 x ULN at any time ALP > 8 x ULN at any time AST or ALT > 8 x ULN at any time AST or ALT > 5 x ULN but < 8 x ULN for ≥ 2 weeks AST or ALT > 3 x ULN with clinical signs or symptoms that are consistent with hepatitis (eg, RUQ abdominal pain/tenderness, fever, nausea, vomiting, jaundice) Permanently discontinue blinatumomab if: 
 TBL > 2 x ULN OR INR > 1.5 (for subjects not on anticoagulant therapy) 
AND
 
 AST or ALT > 3 x ULN (when baseline was < ULN) 
AND
 
 No other cause for the combination of the above laboratory abnormalities is immediately apparent 
Refer to Section 6.7 for additional details

Approved

Footnotes provided on the last page of table

Table 8. Instructions for Treatment Interruption, Dose Modification and Restart

Toxicity	Grade	Instructions for Treatment Interruption and Restart
Other clinically relevant related adverse events ^b	3	
 • Interrupt blinatumomab • Restart blinatumomab at 9 µg/day once improved to grade ≤ 1 or to baseline (refer to Table 7) • Dose step to 28 µg/day after 7 days if toxicity does not recur • Permanently discontinue if: 
 – Initial grade 3 event does not improve to grade ≤ 1 or baseline within 14 days, OR – Grade 3 event reoccurs at the lower dose level within 7 days or reinitiation, OR – Grade 3 event reoccurs at a dose of 9 µg/day without prior step-dose escalation
	4	
 • Permanently discontinue blinatumomab

Page 3 of 3

ALP = alkaline phosphatase; ALT = alanine aminotransferase; AST = aspartate aminotransferase; CRS = cytokine release syndrome; INR = international normalized ratio; RUQ = right upper quadrant; TBL = total bilirubin; ULN = upper limit of normal

Grade scale is based on Common Terminology Criteria for Adverse Events (CTCAE) version 4.03.

^a Obtain brain Magnetic Resonance Imaging (MRI) and perform cerebrospinal fluid (CSF) analysis, if there are no contraindications.

^b For grade 3 or 4 laboratory abnormalities, investigator assessment should be used to determine risk:benefit for each individual patient to continue, interrupt or discontinue blinatumomab treatment.

If the interruption after an adverse event is no longer than 7 days, the same cycle will be continued. The infusion duration before and after an interruption should total 28 days per treatment cycle. If an interruption due to an adverse event is longer than 7 days, a new cycle will start. In addition, an incomplete treatment cycle with a treatment duration of less than 2 weeks will have to be repeated (eg, if cycle 1 was interrupted on day 8 for more than 7 days, the next cycle will be denoted as cycle 1.1 and the same assessments will be performed as in cycle 1). For cycle 1.1, subjects will be started at 9 µg/day for the first 7 days of dosing followed by a dose step to 28 µg/day beginning at day 8 and continuing for the remainder of cycle 1.

In the case of treatment interruptions which do not result in the initiation of a new cycle (ie, < 7 days), all assessments should be completed according to the number of active days on treatment.

Approved

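### Table 8 gives two rules for a grade 4 seizure without saying which governs, and leaves unclear how much of the grade 3 rule applies to seizures

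*Protocol*

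**What the plan says.** Everything at issue is in Table 8 of Protocol Section 6.5, under neurologic events.

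- **Grade 3.** Interrupt for at least 72 hours, give corticosteroids, restart at 9 µg/day after recovery, and step back to 28 µg/day after 7 days if the toxicity does not recur. Three circumstances call for permanent discontinuation. The first is "Initial event occurred at 9 µg/day". The others are failure to improve to grade 1 or lower within 7 days, and recurrence at the lower dose within 7 days of restarting.
- **Grade 4.** "Permanently discontinue blinatumomab". No exception is made for seizures.
- **Seizures.** This line sits in the grade column beside 3 and 4 but carries no grade. It calls for interruption, corticosteroids and anti-seizure medication. On restarting it says "For restart, refer to grade 3 neurologic events above for dose level rules for reinitiation". On timing it says "Do not reinitiate blinatumomab until 7 days after the last seizure and after therapeutic levels of anti-seizure medication are likely to have been achieved". Its own stopping criterion is "Permanently discontinue blinatumomab if a second seizure occurs with reinitiation of blinatumomab at any dose".

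The footnote to the table states: "Grade scale is based on Common Terminology Criteria for Adverse Events (CTCAE) version 4.03". Section 6.2.2 fixes the starting dose: "In the first induction cycle, the initial dose of blinatumomab will be 9 µg/day for the first 7 days of treatment".

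**The concern.** A seizure is a neurologic event and will be graded, since Section 9.2.2.1 applies CTCAE 4.03 to all adverse events. A seizure graded 4 therefore falls under two lines of the same table. One ends treatment and the other leaves a route back to it. A second, lesser difficulty is how far the seizure line's pointer to the grade 3 line reaches.

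This is a safety stopping rule for an event that the protocol expects: the safety summary in Section 2.5.2 names seizure among the neurologic and psychiatric events seen with the drug. About 25 centers (Section 3.2) would apply the table. If they read it differently, one subject could be re-exposed and another permanently stopped after the same kind of event. Withdrawals from blinatumomab due to adverse events are a planned table (Protocol Section 10.4.5, SAP Section 10.6.1), so that count would partly reflect how each site read Table 8.

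**Working it through.** The plan states no figure to reproduce. The check sets the lines of Table 8 against two cases, looks for a precedence rule elsewhere, and then considers size.

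**Case 1: a first seizure, grade 4.**
- Grade 4 line: permanent discontinuation.
- Seizure line: interruption, then possible restart, subject to two conditions. At least 7 days must have passed since the last seizure, and therapeutic anti-seizure levels must be likely. The line has no upper grade limit.
- Result: the two lines lead to different outcomes for the same event.

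**Case 2: a first seizure, below grade 4, while on 9 µg/day.** Subjects are on this dose on days 1 to 7 of cycle 1, and again if restarted at it after another toxicity.
- Reading A: the cross-reference brings in the grade 3 discontinuation criteria. An initial event at 9 µg/day is one of them, so treatment ends.
- Reading B: the cross-reference brings in only the restart dose and the later step to 28 µg/day. The seizure line's own stopping criterion is then a second seizure, so restart is possible.
- Result: the wording admits both readings. The same uncertainty attaches to the other two grade 3 discontinuation criteria.

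**Search for a precedence rule.**
- Table 8 footnotes: one gives the grading scale, one asks for imaging and cerebrospinal fluid analysis after a seizure, and one concerns laboratory abnormalities. None ranks the lines.
- Section 6.5, text after the table: deals with when an interruption leads to a new cycle. It is silent on this point.
- Section 6.6: requires discontinuation for adverse events that meet the protocol's safety criteria. That leads back to Table 8 and does not settle which line applies.

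**Size.** The documents give no seizure rate. Assume 1% to 3% of 120 subjects: 0.01 × 120 = 1.2 and 0.03 × 120 = 3.6, or about 1 to 4 subjects with a seizure of any grade at any dose. Only those with a grade 4 seizure, or with a seizure that meets a grade 3 discontinuation criterion, fall in the disputed area. That subset cannot be larger and may be empty. One subject is 1/120 = 0.8 percentage points of the response rate.

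**The case against.** The best defense of the table is that a specific rule displaces a general one. On that view the seizure line stands in the grade column as an alternative to grades 3 and 4 and governs every seizure. A second defense is that the seizure line never requires restart: it sets conditions for restart if one is contemplated, so a site that stops permanently at grade 4 breaches nothing in it. Both readings are possible, but they point to different practice, and the protocol adopts neither. A site that restarts under the seizure line would still depart from the plain words of the grade 4 line. The gap in precedence stands.

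On the cross-reference the objection has more force. A reader might infer that Table 8 gives opposite instructions for a first seizure at the starting dose. The documents do not support that. The quoted sentence sends the reader to the very line that lists an initial event at 9 µg/day under permanent discontinuation, and that criterion can naturally be called a dose-level rule. The second-seizure criterion is not worded as exclusive and can be read as an addition. The text here is unclear, not contradictory.

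Section 4.1.2 also excludes subjects with a history of epilepsy or seizure, which may keep the number of cases low.

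**Conclusion.** The point holds in two parts of unequal strength. For a grade 4 seizure, Table 8 states two rules with different outcomes and no order of precedence. For the cross-reference to the grade 3 line, the table is ambiguous about whether the permanent-discontinuation criteria are included.

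Several stronger inferences should not be drawn:
- The table does not simply allow restart after 7 days. Seven days is a minimum, and likely therapeutic anti-seizure levels are also required.
- A first seizure at 9 µg/day may be of any grade, so it should not be described as life-threatening as a class.
- Section 2.5.2 says that neurologic and psychiatric events together are most frequent in the first few days. It does not say this of seizures alone.
- Permanent discontinuation does not by itself make a subject a non-responder. Section 6.6 calls for end-of-treatment assessments at once, with bone marrow waived only for documented progression, and Section 10.4.2 counts subjects without a response assessment as non-responders. A stopped subject can still be a responder, although losing further treatment may lower the chance.

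Few or no subjects may be affected, and the 1% to 3% range is an assumption. No alpha, power or sample size figure changes. The reason to act is patient safety and consistent handling across sites.

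**What to change.** The sponsor's medical team should reconcile the lines of Table 8 by stating two things:

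1. Which line governs a seizure that is also grade 4.
2. Whether the seizure line's cross-reference includes the grade 3 criteria for permanent discontinuation, among them an initial event at 9 µg/day, or only the dose at restart and the later step.

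Which rule is right is a clinical decision, and no view on it is offered here. The cost is a short clarification in Table 8, by amendment or site letter. It needs no additional data, no change in sample size and no change to the SAP.
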